5.0 SELECTION AND WITHDRAWAL OF SUBJECTS

5.1 Inclusion Criteria

Patients **must** meet all of the following inclusion criteria before they will be allowed to participate in the trial:

1. Patients with metastatic or advanced, unresectable solid tumor who have progressed, or recurred following standard-of-care (SOC) therapies or are ineligible for, or refuse, safe and effective SOC therapies and for whom, in the opinion of the Investigator, experimental therapy with HS-130/HS-110 may be beneficial.
2. Patients should have lesions that are safely accessible for biopsy and be willing to provide pre-treatment and on-treatment tissue biopsy. Fine-needle aspiration biopsy is not acceptable. Archival

tumor tissue will be accepted in lieu of fresh biopsy at screening if sample was collected within 6-months from Cycle 1 Day 1, and the local pathologist confirms that an adequate amount of tissue/tumor cells exist to allow completion of all testing as outlined in the specimen collection manual.

3. Age \geq 18 years.
4. Have an acceptable organ function:
 - Albumin \geq 2.5 g/dL.
 - Total Bilirubin $<$ 3.0 \times upper limit of normal (ULN) unless patient has Gilbert's syndrome.
 - Alanine transaminase (ALT) and aspartate transaminase (AST) \leq 3.0 \times ULN or \leq 5 \times ULN in the case of liver metastases.
 - Calculated or measured creatinine clearance $>$ 35 mL/minute per the Cockcroft-Gault formula.
 - Absolute neutrophil count \geq 1,500/mm³.
 - Hemoglobin \geq 9 g/dL.
 - Platelet count \geq 100,000/mm³.
5. Have an Eastern Cooperative Oncology Group (ECOG) performance status of 0 or 1.
6. Life expectancy of at least three months.
7. Patients, both females and males, of childbearing/reproductive potential must agree to use adequate contraception while included in the trial and for six months after the last treatment with HS-130 and/or HS-110.
8. Patients must be willing and have the capacity to sign the informed consent form.

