5.2 Exclusion Criteria

Patients **MUST NOT** enter the trial if they meet any of the following exclusion criteria:

1. Have clinically significant cardiac disease, including:
 - Onset of unstable angina within 6 months of signing the Informed Consent Form (ICF).
 - Acute myocardial infarction within 6 months of the signing the ICF.
 - Known congestive heart failure (Grade III or IV as classified by the New York Heart Association); and/ or a known decreased cardiac ejection fraction (LVEF) of $<$ 45%.
 - Uncontrolled hypertension defined as systolic blood pressure \geq 160 mmHg and/or diastolic blood pressure \geq 100 mmHg, despite optimal medical management.
2. Known or clinically suspected leptomeningeal disease. Stable, previously treated metastases in the brain or spinal cord, are allowed as long as these are considered stable (by CT or MRI), and not requiring systemic corticosteroids.

3. History of \geq grade 3 allergic reactions as well as known or suspected allergy or intolerance to any agent given in the course of this trial, live cell therapies, or live vaccines.
4. History of suspected cytokine release syndrome (CRS).
5. Known immunodeficiency disorders (testing not required).
6. Ongoing or current autoimmune disease. Permanent but stable and manageable immune related adverse events (irAE) from prior therapies are permissible, if prednisone equivalent corticosteroid use does not exceed 10 mg/day.
7. Any other condition requiring concurrent systemic immunosuppressive therapy (other than allowable exceptions which do not exceed 10mg/day of prednisone/corticosteroid use).
8. Major surgery (requiring general anesthesia or inpatient hospitalization) within four weeks before first IMP administration.
9. Any ongoing anticancer therapy including; small molecules, immunotherapy, chemotherapy, monoclonal antibodies, radiation (curative/treatment intent) or any other experimental drug. Prior therapy must be stopped within four weeks before first infusion in the study, or 5 half-lives, or twice the duration of the biological effect of the investigational product (whichever is shortest). Adjuvant anti-hormonal treatment(s) for previously treated breast cancer or prostate cancer are allowed. Bisphosphonates are allowed, Denosumab and other RANK ligand inhibitors are prohibited. Note that palliative radiation only requires a two week washout.

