- i: Approximately 23 mL blood per draw Day 1 (pre-dose) and Day 8 for C1 and C2, and at 30-day safety follow-up visit for immune response labs (See Section 8.6).
- j: Cytokines and chemokines sample collection on Day 1 for C1 and C2 at time-points: Before HS130/HS110 treatment, and 2 hr ± 10 minutes after treatment. For C3 and beyond only if the patient is symptomatic i.e. flu-like symptoms, fever, or allergic reactions. (Approximately 3 mL blood per draw).
- k: Pre-treatment biopsy (archival tissue may be submitted if collected less than 6-months prior to C1D1 and the local pathologist confirms that an adequate amount of tissue/tumor cells exist to allow completion of all testing as outlined in the Specimen Collection Manual) and on-treatment biopsy collected within 5-14 days after patient completes 2nd dose of HS-130/HS-110 for genomic and proteomic analysis of exploratory biomarkers (e.g. mIHC). Biopsy should be collected for patients with accessible tumor lesions, incl. metastases (e.g. lymph node metastases) where it is considered feasible without a risk of complications for the patient. Coagulation parameters and blood cells should be assessed and reviewed per institutional standard prior to any biopsy.
- l: HS-130 and HS-110 will be administered via intradermal injections/re-injections (up to 10 total) on Day 1 of each cycle, depending on the assigned dose level. (See section 6.1 Drug preparation and administration)
- m: All assessments should be performed at 30 days ± 3 days after the last treatment, during the 30-day safety follow-up visit.
- n: If a patient stops treatment for any other reason than progressive disease, radiological assessments will continue every 12 weeks starting from the date of patient's last dose until disease progression or initiation of new anti-cancer treatment.
- o: Survival status and subsequent anti-cancer therapy information will be collected approximately every 12 weeks in a clinic visit, or by telephone from the time of disease progression or initiation of new anti-cancer treatment until death.
- p: Each cycle is 14 days.

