7.3.3 Cycle 3 and Beyond (Day 1± 2 days)

- Physical Exam
- Weight
- Vital signs (blood pressure, heart rate, respiratory rate, and temperature only before HS130/HS110 treatment)
- ECG in triplicate (a standard 12-lead ECG is taken while patient is in a semi-recumbent position) (pre-dose)
- ECOG Performance status ([APPENDIX I](#))
- Blood draw for Hematology

- Blood draw for Blood chemistry tests
- Blood draw for Cytokines/Chemokines (Only if patient is symptomatic)
- Record Concomitant medications
- Record Adverse events
- HS-130/HS-110 administration
- On-treatment Biopsy (within 5-14 days after patient completes 2nd dose of HS-130/HS-110). Note that coagulation tests should be reviewed prior to procedure per institutional standards.
- Imaging for tumor measurements by RECIST 1.1¹ (every 8-weeks \pm 1 week from C1D1 until disease progression)

7.4 30-Day Safety Follow up Visit from Last Dose (\pm 3 days)

The following assessments will be performed at 30 days \pm 3 days of the last treatment for all patients who have discontinued treatment with HS-130/HS-110:

- Physical Exam
- Weight
- Vital signs (blood pressure, heart rate, respiratory rate, and temperature)
- ECG in triplicate (a standard 12-lead ECG is taken while patient is in a semi-recumbent position)
- ECOG Performance status ([APPENDIX I](#))
- Blood draw for Hematology
- Blood draw for Blood chemistry tests
- Blood draw for immune response labs (Immunological Effect/Immune re-activation)
- Record Concomitant medications
- Record Adverse events

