8.9 Exploratory Biomarkers

Biopsy samples will be collected from patients during screening/baseline and within 5-14 days after patients have completed second dose of treatment with the HS-130/HS-110 combination drug product. Archival tissue may be substituted for fresh biopsy during screening/baseline, if collected less than 6-

months prior to Cycle 1 Day 1 and the local pathologist confirms that an adequate amount of tissue/tumor cells exist to allow completion of all testing as outlined in the Tumor Biopsy Collection Manual.

Biopsies should only be collected from lesions considered safely accessible, either image-guided or palpable cutaneous or sub-cutaneous lesions. For patients on continuous anticoagulant therapy, study-specific biopsies should not be done unless local guidelines to mitigate the risk of hemorrhage are followed and the procedure can be done with minimal risk for the patient.

Genomic, immunohistochemistry and proteomic analyses of the collected tumor tissue may be performed to identify biomarkers predictive of response or resistance to HS-110/HS-130, for example by multiplex immunohistochemistry (mIHC). Immunohistochemistry analysis using multiplexed immune markers on the collected on-treatment biopsy and could be compared to baseline biopsy to study effect of HS-110/HS-130 combination treatment on patient tumors and could be correlated with clinical response. This exploratory analysis could change in line with scientific understanding and technical development as the clinical study progresses. Please note that pre-treatment and/or post-treatment tissue samples will only be collected if it poses limited risk to the patient.

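### Archival baseline tissue may predate other cancer therapy, so the exploratory paired-biopsy change is not specific to HS-130/HS-110; the biopsy's Cycle 3 listing also needs reconciling with its own window

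*Combined protocol and SAP*

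**What the plan says.** **Baseline tissue.** Section 5.1 item 2 asks for pre-treatment and on-treatment biopsies but allows a substitute: archival "tumor tissue will be accepted in lieu of fresh biopsy at screening if sample was collected within 6-months from Cycle 1 Day 1", provided the local pathologist judges the tissue adequate. Section 7.2, Table 3 footnote k and Section 8.9 repeat the allowance. None of them asks whether other anticancer therapy was given after the sample was taken.

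**Washout.** Section 5.2 criterion 9 reads: "Prior therapy must be stopped within four weeks before first infusion in the study, or 5 half-lives", or twice the duration of biological effect, with the shortest of the three applying. It adds: "Note that palliative radiation only requires a two week washout".

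**Use of the pair.** Section 8.9 says the on-treatment sample "could be compared to baseline biopsy to study effect of HS-110/HS-130 combination treatment on patient tumors", and that the result could be related to clinical response. Section 3.0 lists this work as exploratory.

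**On-treatment biopsy.** Table 3 footnote k calls for an "on-treatment biopsy collected within 5-14 days after patient completes 2nd dose of HS-130/HS-110". The synopsis and Sections 7.3.3, 8.9 and 9.2.3 give the same window. Among the visit lists, however, the biopsy appears only under Cycle 3 and beyond, Day 1 ± 2 days (Section 7.3.3 and Table 3). It is absent from both Cycle 2 lists (7.3.2.1 and 7.3.2.2). In 7.3.3 it comes after the dosing line. The ECG there is marked as pre-dose; the biopsy is not.

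**The concern.** The study has no control arm, so each patient's baseline sample is the only comparator for tissue change. Section 5.1 item 1 admits patients who progressed or recurred after standard therapies. A plausible sequence is tissue taken at one progression, a further line of treatment, failure of that line, washout, then enrollment. The archival sample then describes the tumor before that further line. Any change the line caused is carried into the baseline-to-on-treatment difference and cannot be told apart from an effect of the vaccines. With 13-30 patients over seven dose levels, a few such pairs could shape what is seen, and Section 9 gives no rule for handling them.

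The second issue is smaller. If a site takes the biopsy at the visit where it is listed, the sample may fall after the window closes, or after the third dose, and would then not describe the state after two doses.

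**Working it through.** The plan states no figure for this point, so there is none to reproduce. The check is date arithmetic.

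**1. Therapy that can fall between archival sample and dosing**

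Inputs: archival limit of 6 months (Section 5.1 item 2), taken as 180-183 days; washout of 28 days, or 14 days for palliative radiation (Section 5.2 criterion 9, read as a minimum interval).

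Formula: archival limit minus washout.
- 28-day washout: 180 − 28 = 152 to 183 − 28 = 155 days, about 22 weeks.
- 14-day washout: 180 − 14 = 166 to 183 − 14 = 169 days, about 24 weeks.
- If 5 half-lives is shorter still, the interval is longer.

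Longest gap from baseline to on-treatment sample, with dose 2 given 14 days after C1D1 and the biopsy up to 14 days later:
- Archival: 180 + 14 + 14 = 208 to 183 + 14 + 14 = 211 days.
- Fresh screening biopsy (within 28 days): 28 + 14 + 14 = 56 days.

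**2. Where Cycle 3 Day 1 falls in the biopsy window**

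Inputs: 14-day cycles; ± 2 days on each visit; window of 5-14 days after dose 2. With dose 2 on Day 15, the window is Days 20-29 and nominal C3D1 is Day 29, its last day.

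Formula: days from dose 2 to C3D1 = 14 + (o3 − o2), where o2 and o3 each take the values −2 to +2, giving 25 pairs.

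| Days after dose 2 | Pairs |
|---|---|
| 10-13 | 10 |
| 14 | 5 |
| 15-18 | 10 |

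So 15 of 25 pairs (60%) are inside the window and 10 of 25 (40%) are beyond it. If ± 2 days is counted from the actual second dose, the range is days 12-16 and 3 of 5 offsets are inside. A two-week delay of dose 3, which Section 6.2 permits, moves nominal C3D1 to 14 + 14 = 28 days after dose 2.

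**3. Whether Cycle 2 Day 8 would serve as a fixed visit instead**

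Days after dose 2 = 7 + (o8 − o2), range 3-11. Three of 25 pairs fall before day 5. A fixed visit does not match the window here either.

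**4. First planned scan against the biopsy window**

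The first scan is 8 weeks ± 1 week from C1D1, so no earlier than 49 days after Day 1, which is Day 50. The biopsy window closes on Day 29 if dosing is on schedule. If dose 2 is delayed by two weeks it closes on Day 29 + 14 = 43, still before Day 50.

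**The case against.** The strongest reply is that this is optional exploratory work. Section 8.9 says only that samples could be compared, and it specifies no inferential paired analysis. The archival allowance limits biopsy burden and already has an age limit. The data needed to sort the pairs are also at hand: Section 7.2 collects prior treatments, the 6-month limit requires the sample date, and the washout rule requires the stop date of the last therapy. All of this stands, and it makes the remedy cheap. It does not remove the problem, because the plan nowhere says that those data will be used to separate the pairs. The 22 weeks is a maximum, and the documents do not show how often such a gap would occur.

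On timing, the reply is that the window governs. It is written into the biopsy line of 7.3.3 and into footnote k, so a biopsy on days 5-13 complies. The Cycle 3 column also holds tumor measurement, which is timed by its own footnote and does not fall on C3D1. This stands too. A reader might infer that the biopsy is scheduled at or past the end of its window; the documents do not support that, since nominal C3D1 is inside it and 15 of 25 tolerance pairs comply. What remains is an ambiguous listing and no stated order relative to dose 3.

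A reader might also infer that early progressors would systematically lack an on-treatment sample. The first planned scan comes after the biopsy window has closed, so a patient progressing at that scan has already passed it. Only stops before about Day 29 for other reasons could matter, and the window, counted from dose 2, covers those patients as well.

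**Conclusion.** The baseline point holds. The eligibility and biopsy rules allow up to about 22 weeks of other therapy, or more under the shorter washouts, between the baseline sample and first dosing, and the plan has no step to separate that therapy's effect from that of HS-130/HS-110. The figure assumes that 6 months means 180-183 days and that criterion 9 sets a minimum interval. The number of affected pairs cannot be derived from the documents; it could be anywhere from none to all of the archival pairs.

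The scheduling point holds only as an inconsistency to reconcile: the single listed visit sits nominally on the last permitted day, and its order relative to the third dose is not stated. The 40% figure counts tolerance combinations and would be a probability only if all offsets were equally likely, which is an assumption.

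The impact is confined to the exploratory tissue-biomarker objective. Primary and secondary endpoints are untouched, and the immunologically active dose is assessed from blood. A cheap improvement is warranted.

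**What to change.** **Section 8.9.** State that the paired-change analysis uses only baseline tissue collected after the patient's last prior anticancer therapy, determined from the sample date and the prior-treatment history. Show the remaining pairs separately, flagged with the intervening therapy. Keep older archival tissue for the CTA and shared-antigen work in Section 8.8. No new data collection is needed. The cost is fewer pairs in an already small sample.

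**Table 3 and Section 7.3.** Reconcile the listing with the window: show the on-treatment biopsy as a window-timed item, 5-14 days after dose 2, that starts in Cycle 2, and state that it is taken before dose 3. Let the window govern rather than tying the biopsy to Cycle 2 Day 8, which can itself fall before day 5. This is a text and table edit and adds no biopsy.

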5.2 Exclusion Criteria

Patients **MUST NOT** enter the trial if they meet any of the following exclusion criteria:

1. Have clinically significant cardiac disease, including:
 - Onset of unstable angina within 6 months of signing the Informed Consent Form (ICF).
 - Acute myocardial infarction within 6 months of the signing the ICF.
 - Known congestive heart failure (Grade III or IV as classified by the New York Heart Association); and/ or a known decreased cardiac ejection fraction (LVEF) of $<$ 45%.
 - Uncontrolled hypertension defined as systolic blood pressure \geq 160 mmHg and/or diastolic blood pressure \geq 100 mmHg, despite optimal medical management.
2. Known or clinically suspected leptomeningeal disease. Stable, previously treated metastases in the brain or spinal cord, are allowed as long as these are considered stable (by CT or MRI), and not requiring systemic corticosteroids.

3. History of \geq grade 3 allergic reactions as well as known or suspected allergy or intolerance to any agent given in the course of this trial, live cell therapies, or live vaccines.
4. History of suspected cytokine release syndrome (CRS).
5. Known immunodeficiency disorders (testing not required).
6. Ongoing or current autoimmune disease. Permanent but stable and manageable immune related adverse events (irAE) from prior therapies are permissible, if prednisone equivalent corticosteroid use does not exceed 10 mg/day.
7. Any other condition requiring concurrent systemic immunosuppressive therapy (other than allowable exceptions which do not exceed 10mg/day of prednisone/corticosteroid use).
8. Major surgery (requiring general anesthesia or inpatient hospitalization) within four weeks before first IMP administration.
9. Any ongoing anticancer therapy including; small molecules, immunotherapy, chemotherapy, monoclonal antibodies, radiation (curative/treatment intent) or any other experimental drug. Prior therapy must be stopped within four weeks before first infusion in the study, or 5 half-lives, or twice the duration of the biological effect of the investigational product (whichever is shortest). Adjuvant anti-hormonal treatment(s) for previously treated breast cancer or prostate cancer are allowed. Bisphosphonates are allowed, Denosumab and other RANK ligand inhibitors are prohibited. Note that palliative radiation only requires a two week washout.
10. Known current malignancy other than inclusion diagnosis. Prior curable cancer with complete remission for >2 years is allowed.
11. Any other ongoing significant, uncontrolled medical condition as per Investigator discretion.
12. Received a live vaccine within 30 days prior to first dose of study drug.
13. Clinically significant active viral, bacterial or fungal infection requiring:
 - a. Intravenous treatment with antimicrobial therapy completed less than two weeks prior to first dose, or
 - b. Oral treatment with antimicrobial therapy completed less than one week prior to first dose.Prophylactic treatment with antibiotics (e.g. for dental extractions) is allowed.
14. Known positive serology for human immunodeficiency virus (HIV), hepatitis B, or hepatitis C (except in cases of immunity after cured infection). Testing not required.
15. Substance abuse, medical, psychological or social conditions that may interfere with the patient's participation in the trial or evaluation of the trial result in the opinion of the Investigator.
16. Women who are pregnant or breast feeding.

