7.0 STUDY EVALUATIONS

7.1 Schedule of Study Evaluations

Study evaluations are summarized in [Table 3](#) and described in Sections [1.1](#) through [7.6](#).

Table 3: Schedule of Assessments

	Pre-treatment	Cycle 1 (± 2 days) ^p		Cycle 2 (± 2 days) ^p		Cycle 3 and beyond (± 2 days) ^p	30-day safety follow up visit (±3 days) ^m	Post-treatment Follow-up (±1 week) ⁿ	Survival Follow-up (±2 week) ^o	
		Day 1	Day 8	Day 1	Day 8	Day 1				
Informed consent	X ^a									
Medical history	X ^a									
Physical exam	X ^b	X ^b	X	X	X	X	X			
Weight	X ^b	X ^b	X	X	X	X	X			
Vital signs ^c	X ^b	X	X	X	X	X	X			
ECG ^d	X ^a	X		X		X	X			
ECOG performance status	X ^b	X ^b	X	X	X	X	X			
Tumor measurement ^e	X ^a					X ^e		X ⁿ		
Hematology ^f	X ^b	X ^b		X		X	X			
Blood chemistry ^g	X ^b	X ^b		X		X	X			
Pregnancy test ^h	X ^b									
Blood Sample for Immune Response Labs ⁱ		X ⁱ	X ⁱ	X ⁱ	X ⁱ		X			
Blood sample for cytokines/chemokines ^j		X ⁱ		X ⁱ		X ⁱ				
Biopsy ^k	X ^a					X ^k				
HS-130 and HS-110 administration ^l		X		X		X				
Concomitant medications/Treatment	X ^a	←..... Throughout Study→						X	X	X ^o
Adverse events		←..... Throughout Study→						X	X	
Survival Status									X ^o	

- a: Within 28 days prior to treatment.
- b: Within 7 days prior to treatment. For Cycle 1 Day 1, these tests may be performed within 3 days. Tests done within 3 days of Cycle 1 Day 1 do not need to be repeated unless clinically indicated.
- c: Vital signs, including blood pressure, heart rate, respiratory rate, and temperature. During Cycle 1 and Cycle 2 on Day 1: Before HS130/HS110 treatment; after treatment at 30 mins (± 5 min), 1hr (± 5 min). Other Cycles on Day 1: only Pre-dose.
- d: Standard 12-lead ECG (in triplicate) while patient is in semi-recumbent position pre-dose on Day 1 of each cycle.
- e: Tumor measurement per RECIST 1.1¹. Patients will be evaluated at screening and then after every 8-weeks ± 1 week from C1D1 until disease progression.
- f: Hematology, including hemoglobin, WBC with differential, and platelet count (Approximately 5 mL blood per draw).
- g: Blood chemistry, including sodium, potassium, BUN, glucose, SGOT/SGPT (ALT/AST), alkaline phosphatase, total protein, total bilirubin, albumin, lactate dehydrogenase (LDH), TSH, creatinine, C-reactive protein and calcium. (Approximately 5 mL blood per draw).
- h: Pregnancy test; for women of childbearing potential, a negative pregnancy test (urine or serum) must be documented.

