8.2.1.3 Non-measurable Disease

All other lesions (or sites of disease), including small lesions (longest diameter < 10 mm or pathological lymph nodes with ≥ 10 to < 15 mm short axis) are considered non-measurable disease. Lesions considered truly non-measurable include: leptomeningeal disease, ascites, pleural/pericardial effusions, lymphangitis cutis/pulmonis, inflammatory breast disease, abdominal masses/abdominal organomegaly identified by physical exam and not followed by CT or MRI.

Bone lesions, cystic lesions and lesions previously treated with local therapy must be considered as follows:

Bone lesions:

- Bone scan, PET scan or plain films are not considered adequate imaging techniques to measure bone lesions. However, these techniques can be used to confirm the presence or disappearance of bone lesions.
- Lytic bone lesions or mixed lytic-blastic lesions, with identifiable soft tissue components, that can be evaluated by cross sectional imaging techniques (i.e., CT or MRI) can be considered as measurable lesions if the soft tissue component meets the definition of measurability described above.
- Blastic bone lesions are non-measurable.

Cystic lesions:

- Lesions that meet the criteria for radiographically defined simple cysts should not be considered malignant lesions (neither measurable nor non-measurable) since they are, by definition, simple cysts.
- 'Cystic lesions' thought to represent cystic metastases can be considered measurable lesions, if they meet the definition of measurability described above. However, if non-cystic lesions are present in the same patient, these are preferred for selection as target lesions.

Lesions with prior local treatment:

- Tumor lesions situated in a previously irradiated area, or in an area subjected to other loco-regional therapy, are usually not considered measurable unless there has been demonstrated progression in the lesion.

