8.2.1.7 Guidelines for Evaluation of Measurable Disease

All measurements should be taken and recorded in metric notation using a ruler or calipers. All baseline evaluations should be performed as closely as possible to the beginning of treatment and never more than 4 weeks before the beginning of the treatment.

Target lesions located in a previously irradiated areas should if possible be avoided, but such lesions may be designated as target lesions if clearly progressing (by RECIST 1.1¹ definition) at the latest evaluation prior to screening.

The same method of assessment and the same technique should be used to characterize each identified and reported lesion at baseline and during follow-up. Imaging-based evaluation is preferred to evaluation by clinical examination when both methods have been used to assess the antitumor effect of a treatment.

Clinical lesions. Clinical lesions will only be considered measurable when they are superficial and ≥ 10 mm diameter as assessed using calipers (e.g., skin nodules). In the case of skin lesions, documentation by color photography, including a ruler to estimate the size of the lesion, is recommended. When lesions can be evaluated by both clinical exam and imaging, imaging evaluation should be undertaken since it is more objective and may be reviewed at the end of the study.

Chest x-ray. Chest CT is preferred over chest x-ray, particularly when progression is an important endpoint. Lesions on chest x-ray may be considered measurable if they are clearly defined and surrounded by aerated lung.

Conventional CT and MRI. This guideline has defined measurability of lesions on CT scan based on the assumption that CT slice thickness is 5 mm or less. When CT scans have slice thickness > 5 mm, the minimum size for a measurable lesion should be twice the slice thickness. MRI is acceptable in certain situations (e.g., for body scans).

Ultrasound (US). US should not be used to measure tumor lesions. US examinations cannot be reproduced in their entirety for independent review at a later date because they are operator dependent. If new

lesions are identified by US, confirmation by CT or MRI is advised. If there is concern about radiation exposure at CT, MRI may be used instead of CT.

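### The RECIST baseline scan may predate the end of prior therapy, so tumor change from that therapy can enter best overall response and PFS

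*Combined protocol and SAP*

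**What the plan says.** **End of prior therapy.** Section 5.2, criterion 9 (repeated in the synopsis) says "Prior therapy must be stopped within four weeks before first infusion in the study". It offers two alternatives to the four weeks, five half-lives of the drug or double the time its biological effect lasts, and the shortest of the three applies. It then adds: "Note that palliative radiation only requires a two week washout".

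**Age of the baseline scan.** Table 3 applies note a to tumor measurement: "Within 28 days prior to treatment". Section 7.2 lists imaging in the same 28-day window. Section 8.2.1.7 puts the outer limit at "never more than 4 weeks before the beginning of the treatment". The same sentence asks for baseline evaluations as near to treatment start as can be managed.

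**Irradiated lesions.** Under section 8.2.1.3 a lesion in a previously irradiated area is "usually not considered measurable unless there has been demonstrated progression in the lesion". Section 8.2.1.7 asks that such lesions be avoided as targets where possible, but adds that "such lesions may be designated as target lesions if clearly progressing", judged at the last assessment before screening.

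**How change is scored.** PR is a fall of at least 30% from the baseline sum. PD is a rise of at least 20% and 5 mm from the smallest sum, which may be the baseline sum (8.2.1.8.1). PFS runs from first dose (8.5).

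**The concern.** The scan window and the washout rules were set separately, and no section puts them in order. A patient can be scanned, receive further radiation or drug, and then start HS-130/HS-110 with the earlier scan as the RECIST reference. Change between scan and first dose is then counted as on-study change.

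The error can go either way. Shrinkage from prior therapy makes PR or SD easier to reach. Regrowth after a drug is stopped brings PD closer. With no control arm, nothing in the data would separate either from a vaccine effect. Best overall response and PFS are the endpoints built on tumor measurement (9.2.2), and sections 4.1 and 9.6 say that response by dose level or tumor type may lead to an amendment for expansion cohorts.

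**Working it through.** The plan states no figure for this point, and section 9.6 gives no sample-size calculation, so there is nothing to reproduce. The check is date arithmetic followed by RECIST algebra.

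**Inputs from the protocol:** scan age up to 28 days; palliative radiation washout 14 days; other therapy the shortest of 28 days, 5 half-lives or twice the biological effect; first on-study scan at 8 weeks ± 1 week, that is day 49 to 63 (Table 3 note e); the PR and PD thresholds above. The four-week limb is read as a minimum washout, although its wording is loose.

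**Assumptions (not in the protocol):** half-lives of 0.5 to 4 days; pre-dose shrinkage of 5% to 20%; pre-dose growth of 5% to 15%.

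**Step 1. How far the scan can predate the end of therapy.** Overlap = 28 − washout.

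- Palliative radiation: 28 − 14 = 14 days.
- Drugs, with washout = min(28, 5 × half-life):

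| Half-life (days) | Washout (days) | Maximum overlap (days) |
|---|---|---|
| 0.5 | 2.5 | 25.5 |
| 1 | 5 | 23 |
| 2 | 10 | 18 |
| 4 | 20 | 8 |

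The overlap disappears at a half-life of 28 / 5 = 5.6 days. The drug washout is shorter than the radiation washout below 14 / 5 = 2.8 days. The biological-effect limb can only shorten the washout further.

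**Step 2. Share of the first RECIST interval before any study drug.** With a 28-day-old scan, share = 28 / (28 + day of first scan).

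- Day 49: 28 / 77 = 36%
- Day 56: 28 / 84 = 33%
- Day 63: 28 / 91 = 31%

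**Step 3. Effect on the thresholds.** After unmeasured pre-dose shrinkage s, the on-study shrinkage needed for PR is 1 − 0.70 / (1 − s). After unmeasured pre-dose growth g, the on-study growth needed for PD is 1.20 / (1 + g) − 1, with the 5 mm rule still applying.

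| Pre-dose change | Needed for PR (nominal 30%) | Needed for PD (nominal 20%) |
|---|---|---|
| 5% | 26.3% | 14.3% |
| 10% | 22.2% | 9.1% |
| 15% | 17.6% | 4.3% |
| 20% | 12.5% | not in assumed range |

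The left column is shrinkage for PR and growth for PD. Confirmation at least 4 weeks later (8.2.1.10.1) does not remove the PR error, because it uses the same baseline sum.

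**Step 4. The radiation safeguards.**

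- Sections 8.2.1.3 and 8.2.1.7 concern lesions in areas already irradiated. Section 8.2.1.4 has targets identified and measured at baseline. A lesion scanned on Day −28 and irradiated through Day −14 was not irradiated when measured, and no rule says what then happens to it.
- The exception in 8.2.1.7 looks at progression before screening. Radiation given between that assessment and first dose comes after the progression that qualifies the lesion.
- Section 8.2.1.3 does not say that the progression must follow the radiation.
- Nothing comparable exists for systemic prior therapy.

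**Step 5. Weight of one misattributed response.** It is the whole of a single-patient dose level, 1/3 = 33% of a three-patient cohort, 1/13 = 7.7% of the lower planned enrollment and 1/30 = 3.3% of the upper. The Efficacy Evaluable Population (9.1) may be smaller than enrollment.

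**The case against.** The strongest reply is that the protocol already leans against this. Section 8.2.1.7 asks for scans close to treatment start, so a Day −28 scan followed by more therapy is the worst case. Irradiated lesions are normally kept out of the target sum. By Day 1 the site knows what was irradiated and could exclude the lesion, and progression in an irradiated area is most naturally read as progression after the radiation. The affected endpoints are secondary and every analysis is descriptive.

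Much of this stands. A reader might infer that radiation shrinkage routinely counts as vaccine response. The documents do not support that: 8.2.1.3 and 8.2.1.7 usually prevent it, and the protocol gives no figure for how often a patient is treated between scan and first dose. A reader might also infer that dose selection is at risk. It is not: escalation and MTD rest on DLTs (6.1.1 to 6.1.3), and the RP2D rests on the MTD, the highest feasible dose or possibly an immunologically active dose. Expansion would first need an amendment. Nor does the point show that any washout is too short.

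The reply does not supply an ordering rule. A request to scan close to treatment does not say that the scan follows the last dose, and the exception in 8.2.1.7, followed as written, ties progression to screening, not to the radiation.

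**Conclusion.** The gap is real and narrow. The baseline scan can predate the last palliative fraction by up to 14 days, and the last dose of a drug by about 8 to 25 days for assumed half-lives of 4 to 0.5 days. Prior-therapy tumor change can therefore enter best overall response and PFS; the documents do not show that it will, or how often. It is least guarded for short-half-life systemic drugs. For radiation it remains through the exception in 8.2.1.7 and through lesions irradiated after the scan.

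The day counts are maxima from the stated windows. The threshold shifts depend on the assumed pre-dose changes. The consequence is limited to secondary, descriptive endpoints in very small cohorts and to any expansion that response might prompt. The change is worth making because it is cheap and removes an avoidable source of bias from an uncontrolled response readout.

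**What to change.** 1. In section 8.2.1.7, section 7.2 and Table 3 note e, require the RECIST baseline scan to be taken after the last dose or fraction of prior anticancer therapy, within the existing 28-day window. Note e fits better than note a, which also governs consent, history, ECG and biopsy.
2. In sections 8.2.1.3 and 8.2.1.7, allow an irradiated lesion as a target only if imaging documented its progression after that radiation. State that a lesion irradiated after the baseline scan is followed as non-target.

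The washout lengths are not changed. The maximum time by which the scan can predate the end of therapy falls to 0 days. The cost is wording in a few places, tighter scan timing and occasionally a lost target lesion. Regrowth or delayed shrinkage between the new scan and first dose is reduced but not eliminated; the existing request to scan close to treatment start remains the guard against that.
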